The objective of this study is to identify post-operative CT-based radiological predictors of symptomatic IP tendinopathy in patients with acetabular cup prominence. The analysis compares asymptomatic and symptomatic patients, the latter having undergone arthroscopic tenotomy for IP tendinopathy. All patients were treated at the IRCCS Istituto Ortopedico Rizzoli, Department of Orthopaedics, Trauma and Hip/Knee Arthroplasty and Revision Surgery, between 2000 and 2021.

This is a retrospective observational cohort study. The study population includes adult patients who underwent primary THA and subsequently had a post-operative CT scan performed for pain, clicking, or contralateral hip planning.

Inclusion criteria: primary THA, post-op CT scan available for pain, clicking or contralateral planning; minimum 5-year follow-up for the control group and history of IP tenotomy for the symptomatic group; complete clinical and radiological documentation.

Exclusion criteria: patient refusal; inadequate CT or CT performed for periprosthetic fracture, loosening, infection, or obvious wear; incomplete documentation; insufficient follow-up or resolved symptoms after conservative treatment.

ENDPOINTS AND OUTCOME MEASURES

The primary endpoint is the identification of CT-based radiological predictors of IP tendinopathy in patients with acetabular cup prominence after THA. These include acetabular version, inclination, offset, and reaming technique.

MATERIALS AND METHODS

This study evaluates the radiological predictors of symptomatic IP tendinopathy in a cohort of adults who underwent primary THA and exhibited acetabular cup prominence on post-operative CT. All patients were treated at the IRCCS Istituto Ortopedico Rizzoli between 2000 and 2021. Post-operative CT scans were reviewed, and cases with prominent acetabular cups were selected. Demographic, surgical, and follow-up data were retrieved from the medical records and routine clinical documentation.

Patients were stratified based on the presence or absence of IP tendinopathy. Symptomatic patients had to have undergone IP tenotomy after thorough diagnostic evaluation, including clinical tests, US-guided anesthetic injection (with failed response to multiple infiltrations), serial X-ray, CT, and lab testing to rule out other causes. This diagnostic workflow is supported by the international literature.

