The control group included patients with cup prominence who remained asymptomatic during at least 5 years of follow-up.

COLLECTED VARIABLES

Demographic variables: sex, age at primary THA, operated side, underlying diagnosis.

Implant-related variables: cup type and size, stem type, head diameter, bearing couple, time between THA and CT.

Cup prominence variables: axial and sagittal prominence in mm.

CT-based outcome measures:

- Acetabular version (°)
- Contralateral acetabular version (°)
- Version difference (°)
- Cup inclination (°)
- Femoral offset (mm)
- Acetabular offset (mm)

- Global offset (cm)
- Contralateral global offset (cm)
- Offset difference (cm)
- Acetabular diameter (mm)
- Diameter mismatch (mm)
- Eccentric reaming (mm)

Measurements will be validated through intra- and inter-observer reliability testing. Outcomes will be analyzed to identify radiological predictors of IP tendinopathy. The ultimate goal is to define intraoperative positioning strategies to reduce the risk of developing symptoms.

DATA ANALYSIS

Quantitative variables will be expressed as mean, standard deviation, minimum, and maximum values. Qualitative variables will be reported as frequencies and percentages. Inter- and intra-observer reliability will be assessed using correlation statistics with 95% confidence intervals and standard error. Differences between symptomatic and asymptomatic patients will be evaluated using the Mann-Whitney U test for continuous and discrete variables, and Chi-square test for categorical variables. All analyses will be performed using IBM SPSS version 25 or later. Statistical significance is set at $p < 0.05$.

STUDY TIMELINE

Start date: Date of Ethical Committee (EC) approval.

- Step 1: Kickoff meeting within 2 months of EC approval to plan the project phases, data collection, storage, analysis, and publication.
- Step 2: Data collection from month 2 to 12 post-kickoff.
- Step 3: Data analysis with involvement of all investigators.
- Step 4: Data publication.

End date: Within 18 months from EC approval (12 months for data collection, 6 months for analysis and publication).

DATA COLLECTION AND STORAGE

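### The plan seeks to identify predictors among 12 CT measures, but its only group criterion is an unadjusted p<0.05 with no exploratory label; if none predicts, at least one false predictor arises about 40% of the time (assumed correlations and group sizes)

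*Combined protocol and SAP*

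**What the plan says.** Endpoints and Outcome Measures sets the target: "The primary endpoint is the identification of CT-based radiological predictors of IP tendinopathy in patients with acetabular cup prominence after THA". It then gives an open list of candidates without ranking them: "These include acetabular version, inclination, offset, and reaming technique".

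Collected Variables lists 12 CT-based outcome measures:
- three for version (operated side, other side, difference);
- one for inclination;
- five for offset (femoral, acetabular, global, contralateral global, difference);
- acetabular diameter, diameter mismatch and eccentric reaming.

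The same section says what they are for, "Outcomes will be analyzed to identify radiological predictors of IP tendinopathy", and where the work is meant to lead: "The ultimate goal is to define intraoperative positioning strategies to reduce the risk of developing symptoms".

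Data Analysis gives the method, "Differences between symptomatic and asymptomatic patients will be evaluated using the Mann-Whitney U test for continuous and discrete variables", with Chi-square for categorical variables, and the threshold: "Statistical significance is set at $p < 0.05". All 12 measures carry units of degrees, millimetres or centimetres, so they fall under Mann-Whitney. The only confidence intervals planned are for observer reliability. Neither document section names a primary variable, a testing order, a model, a multiplicity adjustment or an exploratory status for the comparisons.

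**The concern.** The aim is worded as a finding (predictors identified), but the plan supplies only a per-variable significance threshold to support it. The 5% level describes one comparison. It does not describe the statement that at least one of 12 measures has been identified as a predictor. Having several measures per construct, above all five for offset, gives each construct several chances to cross the threshold.

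Without planned effect estimates or intervals for the group differences, a reader of the results could not tell a large, well-estimated difference from a small or imprecise one. Because the protocol looks ahead to positioning strategies, a chance difference could be carried into that goal with nothing in the plan to hold it back.

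**Working it through.** The documents state no sample size, power or family-wise error rate, so there is no figure of the plan's own to reproduce.

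**Inputs from the documents.** Level 0.05 per test (sidedness is not stated; the calculation needs only the level). Four named constructs. Twelve listed CT measures, or ten without the two contralateral values, which can be read as references for the listed differences.

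**Assumed, because not given.** No measure is truly predictive. Groups of 20/40 and 50/100. Side-to-side correlation of 0.3, 0.5 or 0.7.

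**Step 1: independent tests.** P(at least one p<0.05) = 1 − 0.95^k.
- k = 4: 1 − 0.8145 = 18.5%
- k = 10: 1 − 0.5987 = 40.1%
- k = 12: 1 − 0.5404 = 46.0%; expected false positives 12 × 0.05 = 0.6

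**Step 2: why 46% is only an upper reference.** Version difference and offset difference are computed from other listed measures, so the 12 tests cannot all be independent.

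**Step 3: simulation with built-in links.** Mann-Whitney tests under the null, 10,000 replicates per setting (Monte Carlo standard error at most 0.5 points). Model A sets version difference = version − contralateral version, global offset = femoral + acetabular, offset difference = global − contralateral global, and mismatch = diameter − native diameter (correlation 0.7 assumed). Model B adds correlation 0.5 among femoral offset, acetabular offset and diameter, and 0.5 between mismatch and eccentric reaming.

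| Measures tested | Model A | Model B |
|---|---|---|
| All 12 | 40.7-42.1% | 38.1-39.6% |
| 10, no contralateral values | 36.8-37.9% | 33.7-35.7% |

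Across both models, the five offset measures alone give 16.2-18.8%. A separate simulation with side-to-side correlation 0.5 and 3,000 replicates per setting gave 39.2%, 40.8% and 41.0% for groups of 20/40, 30/60 and 50/100. Hence about 40% for the 12 measures.

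**Step 4: stronger correlation.** If all test statistics shared one common correlation r:

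| Tests | r = 0.3 | 0.5 | 0.7 | 0.9 |
|---|---|---|---|---|
| 12 | 39.7% | 31.9% | 23.2% | 13.5% |
| 10 | 35.1% | 28.7% | 21.3% | 12.8% |
| 4 | 17.4% | 15.6% | 13.0% | 9.4% |

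The rate falls as correlation rises but stays above 5% throughout.

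**Step 5: cost of a formal correction.** Holm on four tests starts at 0.05/4 = 0.0125 (critical value 2.498, against 1.960 at 0.05). For a test with an assumed 80% power at 0.05, first-step power is Φ(1.960 + 0.842 − 2.498) = Φ(0.304) = 62%. Keeping 80% would need an effect (2.498 + 0.842)/(1.960 + 0.842) = 1.19 times as large. Baseline powers of 60%, 70% and 90% fall to 39%, 50% and 77%.

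**The case against.** The strongest reply is that the study is exploratory in substance. The protocol describes it thus: "This is a retrospective observational cohort study". Its candidate list is open and it states no confirmatory hypothesis. Such a study need not control the family-wise error rate, and a reader who inferred that the plan breaks a requirement to do so would go too far. That stands. What remains is that the design label describes how data are gathered, not how results are to be read, and nothing in the text limits what p<0.05 may show.

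Three further points also stand in part.

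- No sentence says that a measure with p<0.05 becomes a predictor. A reader might infer a written rule, but the documents only place the aim and the threshold side by side. It is the natural reading because no other between-group criterion is offered.
- A reader might quote 46% as the plan's error rate. The listed measures are linked by construction, so that figure cannot apply.
- The count of 12 is one defensible choice. Acetabular diameter lies outside the four named constructs, while axial and sagittal prominence, listed separately, could face the same tests; 14 independent tests would give 1 − 0.95^14 = 51%. The 18.5% supposes one test per construct, which the plan does not describe.

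It is also fair that labelling the study exploratory leaves these rates unchanged. It changes what may be concluded from a small p-value. Lastly, positioning strategies are an ultimate goal, not a decision that this analysis triggers, so the documents do not support reading a chance finding as leading directly to surgical guidance.

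**Conclusion.** The concern holds in a limited form: an endpoint of identified predictors is paired with an unadjusted per-variable threshold, and neither an interpretive limit nor a planned effect estimate goes with it. The working figure of about 40% depends on three things: that crossing p<0.05 is taken as identification, that no measure is truly predictive, and that the assumed links and group sizes are roughly right. The Introduction reports that other parameters may matter; if some do, the rate for the remaining measures would differ.

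Confidence is high that the plan has no rule or label, and lower on the exact rate. The data and tests remain usable and the gap lies in what may be concluded from them, so the severity is minor to moderate.

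**What to change.** In Data Analysis, add text that does the following:

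1. States that all group comparisons are exploratory and hypothesis-generating.
2. Commits to an effect estimate suited to the Mann-Whitney test (Hodges-Lehmann shift, or area under the ROC curve) with a 95% confidence interval for every CT measure.
3. Commits to reporting all listed measures whatever their p-value.
4. States that p<0.05 alone does not make a measure an identified predictor or a basis for positioning strategies.

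The cost is a little more analysis and a more cautious conclusion, with no new data and no loss of power.

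Holm at a family-wise 0.05 on four variables, one per named construct, is an optional addition. It is suitable only if the investigators can show that the four were chosen before any group comparison was seen. That may be hard in a retrospective study whose Introduction describes the scans as already analysed. It carries the power loss shown in the working, and it guards against chance only: univariable differences that survive Holm may still reflect confounding and do not by themselves establish prediction.
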